7.1.3 Intent-to-treat (ITT) Population

The intent-to-treat population will include all subjects who received at least 1 dose of study drug and at least 1 valid post-randomization assessment of frequency of IA behaviors based on IA diary entry. Subjects will be analyzed according to the treatment they were randomized to.

7.1.4 *Per Protocol (PP) Population*

The per protocol population will include all of the subjects in the ITT population who completed the treatment period (Completed Maintenance Visit 6) with 80% diary completion compliance and who did not have major protocol deviations. Diary compliance is calculated as

diary compliance = $\frac{\text{number of days diary completed within the treatment period}}{\text{Number of treatment days}} \times 100\%$

Detailed specification of the PP population will be provided prior to the database lock for the final analysis.

7.2 Analysis for the Discontinued Treatment Arm

As stated in Section 3.5, the enrollment for the 18 mg arm was discontinued after the interim analysis for Study 810P301, a study separate from this one. As a result, there will be no formal hypothesis tests and statistical comparison between the 18 mg arm and placebo for any efficacy endpoints. However, for completeness in the presentation, 18 mg arm will remain in the table with summary statistics presented.

7.3 Disposition of Subjects

Subject disposition and reasons for screening failure will be summarized for screen-failed subjects (Table 14.1.2.2).

Subject randomization schedule will be listed. Subjects whose randomization codes are unblinded during the conduct of the study will be listed along with the reason for un-blinding (Listing 16.1.7).

The following summaries and listings will be based on all randomized subjects.

Subjects (n and %) who completed and discontinued from the study will be tabulated by the treatment group and study period (titration, maintenance, titration and maintenance combined, and all period combined) for randomized population (Table 14.1.1). The primary reasons for study discontinuation will be included in the tabulation. The primary reasons may include any of the following:

- Subject withdrew consent
- Lost to follow-up
- Administrative reason
- Adverse event
- Investigator decision

- Failure to follow required study procedures
- Other

Also, subject's enrollment will be summarized by study site among ITT population (Table 14.1.2.3).

A data listing will be presented for subject's disposition and reasons for discontinuation (Listing 16.2.1.1).

7.4 *Protocol Deviations*

Protocol deviations will include, but are not limited to

- Non-compliance with any scheduled study visit
- Non-compliance with study treatment
- Prohibited medications
- Non-compliance with study inclusion or exclusion criteria
- Non-compliance with study assessment procedures

Subjects with major protocol deviations will be listed based on all randomized subjects. The listing will include a brief description of the deviation, deviation category, and if applicable, study day when deviation occurred along with other pertinent information (Listing 16.2.1.2).

If warranted, subjects (n and %) with major protocol deviations will be tabulated by treatment group and deviation category for ITT population (Table 14.1.2.4).

Subject's inclusion/exclusion from each analysis population will be listed along with the applicable reasons for exclusion (Listing 16.2.1.3).

7.5 Demographics and Baseline Subject Characteristics

Subject age, sex, ethnicity, race, height at screening, weight at screening and baseline will be summarized based on the ITT population by treatment group. Age will be summarized as a continuous variable as well as a categorical variable (6 to 9 [i.e., <10], and 10 to 12 [i.e., \geq 10 and \leq 12] years, inclusive) (Table 14.1.2.1).

All demographic and baseline characteristics will be included in the subject data listing (Listing 16.2.1.4).

7.6 Baseline Disease Characteristics

Summaries of baseline disease characteristics will be based on the ITT population, except for medical history, which will be based on the Safety population.

Subject incidence (n and %) of medical history will be tabulated by MedDRA System Organ Class (SOC) and Preferred Term (PT) for each treatment group as per Section 7.9.1 (Table 14.1.3.1).

R-MOAS (item, and domain scores [Table 14.1.5.1.1and Table 14.1.5.1.2]) and Vitiello Aggression Scale (item, and domain scores [Table 14.1.5.2.1 and Table 14.1.5.2.2]) will be summarized by treatment group as per Section 6.1.

All baseline disease characteristics will be listed (Listing 16.2.1.5 – Listing 16.2.1.7).

7.7 Treatments

7.7.1 Treatment Compliance and Extent of Exposure

Summaries of treatment compliance and exposure will be based on the ITT population.

Duration of exposure is defined as the total number of days a subject is exposed to any study treatment. This will be calculated for each subject by taking the difference between the date of last dose minus the date of the first dose, plus 1 (date of last dose – date of first dose +1).

Duration of Treatment exposure will be summarized using descriptive statistics (n, mean, SD, median, minimum, and maximum).

Percent of SM compliance is defined as

Treatment Compliance = $\frac{\text{Number of Tablets Dispensed} - \text{Number of Tablets Returned}}{4x(\text{Date of Last Dose} - \text{Date of First Dose} + 1)} \cdot 100\%.$

Each subject is expected to take 4 tablets per day as in the following. Subjects randomized to placebo group will take 2 placebo tablets in the morning and 2 placebo tablets in the evening. Subjects randomized to SPN-810 18 mg will take one 9 mg active tablet and 1 placebo tablet in the morning and one 9 mg active tablet and 1 placebo tablet in the evening. Subjects randomized to SPN-810 36 mg will take two 9 mg active tablets in the morning and two 9 mg active tablets in the evening. For each treatment, SM compliance will be summarized with number of subjects (n and %) by compliance category (<80%, 80-120%, and >120%). SM compliance will also be summarized as a continuous variable using descriptive statistics (n, mean, standard deviation, median, minimum, and maximum) for each treatment.

Summaries of treatment compliance and exposure will be presented separately for the Titration Period, Maintenance Period, and combined Titration and Maintenance Periods (Table 14.1.4 and Listing 16.2.1.8).

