## 3.2.3 Conversion/Taper Phase

All subjects who complete the randomized, double blind portion of study 810P302 will have the option to participate in an OLE study (study protocol 810P304) in which all subjects will receive active SM treatment. Subjects choosing to participate will receive blinded conversion medication kits, and their total daily dose for the open label extension will be converted to 18 mg/day (Figure 1). Those subjects who do not elect to participate in this extension will be tapered off SM (Figure 2).

[figure not shown]
The 18 mg line in the 2 figures below will not be applicable to subjects re-randomized following the 810P301 interim analysis decision to drop the 18 mg dose.

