7.1.1 Safety Population

The safety population will include all randomized subjects who received at least 1 dose of study drug and have at least one post-randomization safety measurements.

7.1.2 *Modified Intent-to-treat (mITT) Population*

The modified intent-to-treat population will include all subjects who received at least 1 dose of study drug and have a baseline IA frequency \geq 6 per week and at least 1 valid post-randomization assessment of frequency of IA behaviors based on IA diary entry. Subjects will be analyzed according to the treatment they were randomized to.

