7.9 Safety Analyses

Subject safety is assessed by AEs, labs, vital signs, 12-lead ECGs, and findings from the physical examinations. The occurrence of neurological side effects will be assessed by looking at any worsening in scores for each of the Simpson-Angus scale, Barnes Akathisia scale, and AIMS. Suicidal ideation and suicidal behavior will be measured by C-SSRS. All summaries related to safety analyses will use the safety population and will be presented by treatment groups.

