Appendix 1. Exclusion Criteria for the Per Protocol Populations

Appendix 2. List of Tables, Listings, and Figures

| Tables |
|---|
| Table 14.1.1 Summary of Subject Disposition and Reason for Discontinuation by Treatment Group and |
| Period (Randomized Population) |
| Table 14.1.2.1 Demographics and Baseline Characteristics (ITT Population) |
| Table 14.1.2.2 Subject Demographic Characteristics and Reason for Screening Failure (Screening |
| Failure Subjects) |
| Table 14.1.2.3 Subject Enrollment Distribution by Study Site (ITT Population) |
| Table 14.1.2.4 Summary of Major Protocol Deviations During the Study, by Treatment Group (ITT |
| Population) |
| Table 14.1.3.1 Medical History by System Organ Class and Preferred Term (Safety Population) |
| Table 14.1.3.2 Prior Medications by ATC Code and Preferred Term (Safety Population) |
| Table 14.1.3.3 Concomitant Medications by ATC Code and Preferred Term (Safety Population) |
| Table 14.1.3.4 Subjects with ≥5% Allowed Concomitant Medications by ATC Code and Preferred Term |
| (Safety Population) |
| Table 14.1.4 Exposure to Study Medication and Compliance (ITT Population) |
| Table 14.1.5.1.1 Retrospective Modified Overt Aggression Scale at Baseline – Item Scores (ITT |
| Population) |
| Table 14.1.5.1.2 Retrospective Modified Overt Aggression Scale at Baseline – Domain and Total Scores |
| (ITT Population) |
| Table 14.1.5.2.1 Vitiello Aggression Scale (VAS) at Baseline – Item Scores (ITT Population) |
| Table 14.1.5.2.2 Vitiello Aggression Scale (VAS) at Baseline – Domain and Total Scores (ITT Population) |
| Section 14.2 – Efficacy Tables |
| Table 14.2.1.1 Percent Change from Baseline in the Average Weekly Frequency of IA Behaviors During |
| the Treatment Period [1] - (mITT and ITT Population) |
| Table 14.2.1.2.1 Percent Change from Baseline in the Average Weekly Frequency of IA Behaviors |
| During the Treatment Period [1] - Sensitivity Analysis, Multiple Imputation with MAR Assumption (mITT |
| and ITT Population) |
| Table 14.2.1.2.2 Percent Change from Baseline in the Average Weekly Frequency of IA Behaviors |
| During the Treatment Period [1] – Sensitivity Analysis, Multiple Imputation (mITT and ITT Population) |
| Table 14.2.1.2.3 Percent Change from Baseline in the Average Weekly Frequency of IA Behaviors |
| During the Maintenance Period - Sensitivity Analysis (mITT and ITT Population) |
| Table 14.2.1.3 Percent Change from Baseline to Treatment Period in Frequency of IA Behaviors: |

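### Extent of exposure is summarised on the diary-based ITT population while adverse events use the Safety population, so some of the shortest exposures can drop out of the exposure table

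*SAP*

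**What the plan says.** SAP 7.7.1 sets the analysis set for both topics in one sentence: "Summaries of treatment compliance and exposure will be based on the ITT population". The table list in SAP Appendix 2 repeats it for Table 14.1.4: "Exposure to Study Medication and Compliance (ITT Population").

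The ITT definition in SAP 7.1.3 requires a dose and "at least 1 valid post-randomization assessment of frequency of IA behaviors based on IA diary entry". SAP 7.1.1 defines the other set: "The safety population will include all randomized subjects who received at least 1 dose of study drug and have at least one post-randomization safety measurements". SAP 7.9 then says: "All summaries related to safety analyses will use the safety population".

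On duration, SAP 7.7.1 says: "Duration of exposure is defined as the total number of days a subject is exposed to any study treatment". It computes this as last dose date minus first dose date plus 1. The section closes by limiting the exposure and compliance summaries to titration, maintenance and the two combined, and Protocol 6.7 does the same. Protocol 6.7 names no analysis set for exposure.

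**The concern.** An exposure table tells the reader how long the children in the adverse event tables were on drug. It does that only if both tables describe the same children. Here one is filtered by diary completion and the other is not. The filter also bears on duration: a child with no diary assessment after randomisation is most likely one who stopped within the first days. Such a child's adverse events would be counted while the short exposure would not.

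Exposure stands out among the related summaries. Medical history (SAP 7.6) and prior and concomitant medications (SAP 7.7.2) are already on the Safety population.

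At stake is a safety description: the mean, median and minimum duration by arm, and the match between the number of children in the exposure table and in the adverse event tables.

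**Working it through.** **Step 1. Who falls in which set.** Applying SAP 7.1.1 and 7.1.3 to a randomised child who took at least one dose:

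| Valid diary assessment after randomisation | Safety measurement after randomisation | In adverse event tables (Safety) | In exposure table (ITT) |
|---|---|---|---|
| yes | yes | yes | yes |
| no | yes | yes | **no** |
| yes | no | no | yes |
| no | no | no | no |

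The second row is the problem. The last two rows show that the SAP Safety set does not hold every dosed child either. The Safety population in Protocol 6.3 needs only a dose, so it would hold all four rows.

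**Step 2. Whether the second row can occur.** Protocol 4.2.7 and 4.6 have early discontinuers complete Visit 7, with movement scales, C-SSRS, laboratory tests and adverse event collection. That visit supplies the safety measurement. On the diary side, the SAP Section 4 definitions place entries up to and including Day 1 in the baseline period, and titration diaries start after Visit 3. A child who stops around Day 1 with no later diary entry can therefore have a safety measurement and no treatment-period diary. The SAP does not say whether an entry made on Day 1 after dosing would count as valid for ITT.

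**Step 3. Size.** The plan's reference duration reproduces: 2 weeks of titration (14 days) plus 3 weeks of maintenance (21 days) gives 14 + 21 = 35 days, the stated 5 weeks. The visit schedule agrees, since Day 36 − Day 1 = 35.

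The documents give no count of dosed children without a diary assessment, so the effect can only be shown over a range. Three assumptions are needed:
- the ITT mean is 32 days, somewhat below 35 because some children stop early;
- each omitted child had 2 days of exposure;
- the omitted fraction *f* of dosed children is 0.5% to 5%.

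Mean over all dosed children = (1 − *f*) × 32 + *f* × 2. Overstatement = 32 / that mean − 1.

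| *f* | Mean, all dosed (days) | Overstatement of the mean |
|---|---|---|
| 0.5% | 31.85 | 0.5% |
| 1% | 31.70 | 0.9% |
| 2% | 31.40 | 1.9% |
| 5% | 30.50 | 4.9% |

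Of about 306 randomised children, this range corresponds to roughly 2 (0.005 × 306 = 1.5) to 15 (0.05 × 306 = 15.3). The reported minimum could be affected by a single omitted child.

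**Step 4. Periods covered.** SAP 7.9.1 tabulates adverse events by titration, maintenance, the two combined, and tapering. SAP 7.7.1 lists the first three only. Tapering-period adverse events therefore have no matching exposure summary.

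**The case against.** The case for leaving this alone is fair. One valid diary assessment is enough for ITT, and every randomised caregiver has already shown at least 80% diary compliance at baseline (12 of 15 days), so very few children should be lost. They are not hidden: Listing 16.2.1.8, paired with Table 14.1.4, covers the randomised population, and disposition by period also uses all randomised subjects. The adverse event tables report subject incidence with no exposure-adjusted rate, so exposure is not the denominator of any planned figure. Moving to the SAP Safety set might not recover every early stopper, because that set has its own post-randomisation condition.

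All of this stands as an argument about size. It does not remove the mismatch: a listing is not a summary, and the summary is what readers will set beside the adverse event tables.

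A reader might also infer something stronger. The duration formula covers any study treatment, and conversion or taper medication is dispensed at Visit 6. A completer's exposure might then seem to run to about Day 42, overstating it by 20% (42/35 = 1.20), with perfect compliance reading 83% (140/168). The documents do not support this, for three reasons.
- SAP 7.7.1 and Protocol 6.7 limit the summaries to titration, maintenance and the two combined, and SAP 3.3.2 lists conversion/tapering as a separate phase.
- The 83% divides titration and maintenance tablets (4 × 35 = 140) by days that include the extra week (4 × 42 = 168). The SAP numerator is tablets dispensed minus returned, so the extra week's tablets would enter it too. At 4 per day that gives 168/168 = 100%.
- The 35 days include 14 days of titration, so the ratio does not measure time on the randomised dose.

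What remains is missing detail. SAP 7.7.1 does not say how dose dates are cut at Visits 5 and 6. SAP Section 4 defines the periods for diaries only. The one named source of the last-dose date is the End of Study page, in a SAP 6.4 rule for children who discontinue. Protocol 4.3.6 also speaks of a 6-week treatment phase against 5 weeks in the synopsis and SAP 3.3.2. These should be reconciled.

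**Conclusion.** The point holds and is minor. Under the SAP's own definitions, a dosed child with a safety measurement but no valid diary assessment counts in adverse event incidence and is left out of exposure, so the exposure table can omit some of the shortest durations. The number is unknown and probably small. The 0.5% to 4.9% range for the mean rests wholly on the assumed 32-day mean, the 2-day exposures and the 0.5% to 5% omitted fraction. The documents supply none of these.

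The handling of dose dates at Visits 5 and 6, and the lack of a conversion/taper exposure line, are points to clarify. They are not evidence that exposure is overstated. No efficacy analysis is affected.

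**What to change.** In SAP 7.7.1 and the title of Table 14.1.4, base extent of exposure on the Safety population. Using all dosed subjects would be better still, because SAP 7.1.1 also requires a post-randomisation safety measurement, and all dosed subjects is how Protocol 6.3 defines its Safety population. Compliance may stay on ITT, provided the table labels the two sets.

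As clarifications in the same section:
- state that first and last dose dates are cut at Visit 5 and Visit 6 for the titration, maintenance and combined summaries;
- add a separate conversion/taper exposure line to match the tapering-period adverse event table in SAP 7.9.1.

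The cost is a few sentences of SAP text and re-programming of Table 14.1.4. No new data are needed beyond the dose dates by period.

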7.7.2 Prior and Concomitant Medications

Prior and concomitant medications will be tabulated separately based on the Safety Population. The number (n and %) of subjects taking at least one medication and the number (%) of subjects taking each medication at the WHODD preferred term level will be tabulated by treatment group, Anatomical-Therapeutic-Chemical classification 4 (ATC4), and PT. Subjects taking the same PT medication twice will only be counted once (Table 14.1.3.2 and Table 14.1.3.3). In addition, the number and percent for subjects with \geq 5% allowed concomitant medications by ATC code and preferred term will be reported (Table 14.1.3.4).

A subject data listing will be provided to include the reported medication name, the WHODD PT, ATC4, study day and pertinent subject information (Listing 16.2.1.9.1 and Listing 16.2.1.9.2).

A separate data listing will include subjects who received prohibited medications (Listing 16.2.1.9.3).

7.8 *Efficacy* Analyses

7.8.1 Primary Efficacy Analysis

The primary analysis will be based on the mITT population and the primary efficacy endpoint is percent change (PCH_T) in the frequency (unweighted score) of IA behaviors per 7 days in the treatment period relative to the Baseline period calculated over the number of days with non-missing IA diary. The analysis will be repeated for the ITT population, which follows the original primary efficacy analysis population definition.

Both of the above analyses will be performed using the Wilcoxon rank-sum test to compare the median SPN-810 36 mg with the median of the Placebo. The Hodges-Lehmann estimate of the difference (SPN-810 36 mg dose minus placebo) and the associated 95% confidence interval (CI) around the difference will be calculated. The statistical analysis will be presented in the table along with the summary of the change from baseline frequency (Table 14.2.1.1). The daily IA behavior diary will be listed. The daily frequency, the derived 7-day frequency for each week, and the derived 7-day frequency for the treatment period will be included (Listing 16.2.2.1.1 – Listing 16.2.2.1.2). Histogram of median percent change from baseline in the frequency of IA Behaviors in treatment will be created for 36 mg dose and Placebo (Figure 14.2.1.1).

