# 6.9 Efficacy Analyses

# 6.9.1 Primary Efficacy Analysis

The primary efficacy endpoint is the percent change  $(PCH_T)$  in the frequency (unweighted score) of IA behaviors per 7 days in the Treatment (Titration and Maintenance) period relative to the Baseline period calculated over the number of days with non-missing IA diary data. The frequency of IA behaviors per 7 days is the sum of scores for all events in a given period of sequential days, adjusted to 7 days.

The primary efficacy endpoint  $PCH_T$  will be calculated by  $PCH_T = 100^*(T - B)/B$ , where T and B are IA behavior frequencies per 7 days during the treatment period and baseline period, respectively. The IA behavior frequency per 7 days is defined as (SUM/DAY) x 7, where SUM is the sum of the IA behaviors reported in the subject IA diary, and DAY is the number of days with non-missing IA frequency data in the subject IA diary during the specified study period.

Per the adaptive design feature of protocol 810P301 that led to discontinuation of the 18 mg dose group, SPN-810 36 mg vs. placebo will be tested.

The null  $(H_0)$  and the alternative  $(H_a)$  hypotheses are as in the following:

- H01: There is no difference between the median of the 36 mg dose SPN-810 and the median of placebo vs.
- $H_{a1}$ : There is a difference between the median of the 36 mg dose SPN-810 and the median of placebo.

The primary efficacy analysis will be performed using the Wilcoxon rank-sum test to compare the median of 36 mg dose of SPN-810 with the median of the Placebo. The Hodges-Lehmann estimate and the associated 95% confidence interval (CI) will be calculated. The superiority of 36 mg dose to placebo will be claimed if the p-value from this analysis < 0.05 at alpha of 5% significance level. There is no multiplicity adjustment with respect to the primary endpoint since only 2 treatments are compared.

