# 6.10 Sample Size and Power Considerations

Based on results from the Phase 2 study, a 15-point average difference in favor of the SPN-810 treatment arms compared with placebo is assumed; the change from baseline to endpoint in total R-MOAS rating was used to evaluate the difference. The R-MOAS was used because there have been no prior studies with the IA diary. A common standard deviation of 34.83 was obtained from a blinded analysis of SPN-810P301 data.

Based on these parameter assumptions, a sample size of approximately 122 per arm will yield 90% power to detect a non-zero difference between the median of SPN-810 treatment and the placebo groups using the Wilcoxon rank-sum test with a 2-sided significance level  $\alpha$ =0.05.

The original sample size of 291 was based on having 3 treatment groups (97 subjects per arm) and specific assumptions on the drug placebo difference, standard deviation and discontinuation rate.

CONFIDENTIAL Version 7.0

[figure not shown]
After the 810P301 study Interim Analysis result was completed, the 18 mg dose arm was discontinued and subjects planned to be randomized to the 18 mg arm would be re-allocated to the 36 mg or placebo arm in a ratio of 2:1. As such there will be an unequal randomization between the 36 mg dose group and placebo. With this post-interim analysis un-equal randomization, the placebo arm is expected to approach approximately 121 subjects of the total of 306 subjects randomized.

The sample size was calculated using the nQuery Advisor Software, Version 7.

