3.5 Determination of Sample Size

The original sample size was based on the results from the Phase 2 study. It was assumed that the average treatment difference between SPN-810 dose groups and placebo is 15 with a common standard deviation (SD) =27.3. A sample size of 77 subjects per arm (1:1:1 allocation ratio) would yield 90% power to detect a non-zero difference between the median of 18 mg or 36 mg dose group and the placebo using the Wilcoxon rank-sum test with a 2-sided significance level of alpha=0.05.

After the interim analysis for Study 810P301, the 18 mg dose arm was discontinued for randomization. Subjects planned to be randomized to the 18 mg arm were re-randomized to the 36 mg or placebo arms at a 2:1 allocation ratio. A blinded review of the 810P301 data indicates that the SD for the interim data was actually 34.83 instead of the protocol assumed 27.3. This new SD leads to a total sample size of 306 (adjusted for 20% attrition) subjects. Approximately 167 subjects were randomized prior to the implementation of the 2:1 randomization. It follows that 139 subjects would be randomized in a 2:1 ratio of 36 mg to following the re-calculation of sample size with the new SD.

The sample size was calculated using the nQuery Advisor Software, Version 7.

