5.1 Primary Efficacy Variable

The primary efficacy endpoint is percent change (PCH_T) in the frequency (unweighted score) of IA behaviors per 7 days in the treatment (titration and maintenance) period relative to the Baseline period calculated over the number of days with non-missing IA diary data.

PCH_T will be calculated as 100 x (T – B)/B, where T and B are IA behavior frequencies per 7 days during the treatment period and baseline period, respectively. The IA behavior frequency per 7 days is defined as (SUM/DAY) x 7, where SUM is the total of the IA behaviors reported in the subject IA diary, and DAY is the number of days with non-missing IA score in the subject IA diary during the specified study period.

This primary efficacy variable will be based on a checklist of 15 IA behaviors collected in an electronic IA diary. The IA diary comprises two parts: 1) an episodic diary that will be used by the primary caregiver (or alternate) to enter events as soon as possible after they are observed; and 2) an evening diary that will prompt the caregiver to review events for the day and to enter any events that were not previously captured. Each event will be characterized by a checklist of 15 observed behaviors: Yelling, Screaming, Threatening, Scratching, Throwing, Slamming, Hitting Self, Arguing, Cursing, Name Calling, Shoving, Hair Pulling, Fighting, Hitting Others, and Kicking Others. The checklist will indicate whether each behavior was observed (coded 1) or was not observed (coded 0) during the incidence of an event. Each day can have multiple events. A day can have no event, as can be attested in the evening diary. In this case, if no event is reported

during a day, and the evening diary confirms this, the daily event score for that subject will be 0 for each of the 15 IA variables. Behaviors not on this list will not be captured.

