6.3 Adjustment for Covariates

An exploratory analysis of the primary efficacy endpoint will be performed using a randomization-based approach (Dmitrienko and Koch 2017). This analysis will include age (categorical and continuous), gender, pooled site and baseline IA adjusted to 7 days as covariates.

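### The primary Wilcoxon test on percent change is valid and meets its planned power, but it leaves baseline IA frequency unadjusted; adjusting could add power at no cost in patients, by an amount the documents do not fix

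*SAP*

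**What the plan says.** Protocol 6.9.1 and SAP 7.8.1 specify the same confirmatory test. The protocol states: "The primary efficacy analysis will be performed using the Wilcoxon rank-sum test to compare the median of 36 mg dose of SPN-810" with placebo. The SAP runs it on the mITT population and repeats it on the ITT population: "Both of the above analyses will be performed using the Wilcoxon rank-sum test to compare the median SPN-810 36 mg". Neither version has a covariate.

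The endpoint is PCH_T = 100 x (T - B)/B, "where T and B are IA behavior frequencies per 7 days during the treatment period and baseline period, respectively" (SAP 5.1). Baseline therefore acts in the primary analysis only as the divisor.

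The SAP does plan a baseline-adjusted analysis of the same endpoint. Section 6.3 describes a randomization-based approach: "This analysis will include age (categorical and continuous), gender, pooled site and baseline IA adjusted to 7 days as covariates". Section 7.8.4 gives the macro call, and Table 14.2.1.3 is listed for both mITT and ITT. Both sections label the analysis exploratory.

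The secondary scale analyses are handled differently. The MMRM for change in CGI-S includes baseline (SAP 7.8.6.1). In SAP 7.8.6.2 the CGI-I model uses CGI-S as its baseline covariate, and CHQ-PF28, PSI-4-SF and SNAP-IV are analysed by ANCOVA with baseline.

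**The concern.** The diary baseline runs for at least 15 days with at least 80% completion (Protocol 3.2.1.2), so a direct pre-treatment measure of the primary outcome is in hand. Using a percent change can look like sufficient adjustment. It is sufficient only when a child's expected treatment-period frequency is a constant multiple of the baseline frequency. With regression to the mean, a child whose baseline was high by chance shows a larger percent fall in either arm, so PCH_T remains correlated with B.

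Regression to the mean is plausible here. Children enter on high severity scores (Protocol 4.1.1), and the mITT population is cut on observed baseline frequency (SAP 7.1.2). The sponsor's own CGI-S analysis includes baseline although its response is already a change score, and no reason is given for treating the primary endpoint differently.

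What is at stake is the efficiency of the one confirmatory test, and whether its p-value responds to a chance baseline imbalance between the arms.

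**Working it through.** **Inputs.** From Protocol 6.10: "a 15-point average difference in favor of the SPN-810 treatment arms compared with placebo is assumed"; "A common standard deviation of 34.83 was obtained from a blinded analysis of SPN-810P301 data"; "a sample size of approximately 122 per arm will yield 90% power to detect a non-zero difference". From SAP 3.5, the test is set up "using the Wilcoxon rank-sum test with a 2-sided significance level of alpha=0.05". I read 34.83 as the unadjusted SD of PCH_T. The correlation rho between baseline IA frequency and PCH_T is in neither document, so it is an assumption and is varied below.

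**Step 1: reproduce the plan's figure.** Noether's formula for the Wilcoxon test with equal arms:

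- p = Phi(15 / (34.83 x sqrt 2)) = Phi(0.3045) = 0.6196
- N = (1.960 + 1.282)^2 / (12 x 0.25 x 0.1196^2) = 244.7, or 122.4 per arm

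This matches 122. With the original SD of 27.3 the same formula gives 76.6, matching 77. Allowing for 20% attrition, 122/0.8 rounds up to 153 per arm, or 306 in total. At 122 per arm the computed power is 89.9%.

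**Step 2: power after adjustment.** Adjusting for a covariate with correlation rho multiplies the SD by sqrt(1 - rho^2). Applying this to the rank test is an approximation. At 122 per arm:

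| abs(rho) | Adjusted SD | p | Power | Gain (points) |
|---|---|---|---|---|
| 0 | 34.83 | 0.6196 | 89.9% | 0 |
| 0.1 | 34.66 | 0.6202 | 90.2% | 0.3 |
| 0.2 | 34.13 | 0.6220 | 91.0% | 1.1 |
| 0.3 | 33.23 | 0.6252 | 92.3% | 2.4 |
| 0.4 | 31.92 | 0.6302 | 94.1% | 4.2 |
| 0.5 | 30.16 | 0.6374 | 96.1% | 6.2 |

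**Step 3: what rho might be.** Suppose log B and log T have equal variance and correlation r. Then log(T/B) correlates with log B at -sqrt((1 - r)/2): -0.50 at r = 0.5, -0.39 at 0.7, -0.32 at 0.8 and -0.22 at 0.9.

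If the treatment-period log SD is q times the baseline log SD, then rho = (rq - 1) / sqrt(q^2 + 1 - 2rq). At r = 0.7 the gain is 3.9 points with q = 1, 0.9 with q = 1.2 and 0.3 with q = 1.3. It is zero when rq = 1, which is the proportional case.

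**Step 4: simulation check.** I simulated Poisson diary counts with a baseline median of 40 per week and log SD of 0.8 (both assumed), equal variances, 15 baseline and 35 treatment days, the mITT cut, 122 per arm, and the effect set so that Wilcoxon power was about 90%. Rank ANCOVA gained 5.8 points at r = 0.5, 3.5 at 0.7, 2.2 at 0.8 and 1.4 at 0.9. In a similar simulation with a median of 35, type I error was 4.8% for both tests.

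**Step 5: arm sizes.** The documents leave unclear whether 306 counts the 18 mg subjects. If it does, and 20% are lost, the arms are about 94 and 106: unadjusted power is 83.3%, and the gains at rho 0.4 and 0.5 are 5.6 and 8.7 points. If it does not, the arms are 121 and 185 before losses: power starts at about 94%, and the gains are 2.8 and 3.9 points.

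**The case against.** The strongest reply is that this is a preference about efficiency. The unadjusted Wilcoxon test is valid under randomization, and its null distribution already allows for chance baseline imbalance. The trial was sized on exactly this test, and the planned 90% is met. All of that stands.

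The size of the gain is also open to challenge. If 34.83 is the SD of PCH_T, frequencies are lognormal with log SD 0.8 and equal variances, and the median T/B is 0.5 to 0.7, then r = 0.5 would imply an SD of about 65 to 91. Matching 34.83 needs r of about 0.76 to 0.85, hence |rho| of about 0.27 to 0.35 and a gain of 2.0 to 3.2 points. Those inputs are themselves assumed: letting log SD run from 0.6 to 1.0 and median T/B from 0.4 to 0.8 widens the gain to 1.0 to 6.8 points. This is a fair reason to quote a conditional range.

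Finally, the change is more than a line of code. The MAR imputation analysis (Protocol 6.9.4.1, SAP 7.8.2.1) runs the Wilcoxon test on each imputed dataset and pools Hodges-Lehmann intervals, and SAP 7.8.2.3 repeats the primary analysis on maintenance data. Version 2.1 of the SAP has already altered the primary population, so a further late change needs a clear justification. These points raise the cost somewhat, but they do not remove the improvement.

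**Conclusion.** The primary test is sound and powered as stated, but it does not use baseline IA frequency beyond the divisor. Under the plan's inputs, adjustment would add about 1 to 6 points of power for |rho| between 0.2 and 0.5, and nothing at rho 0. This rests on 122 evaluable subjects per arm, on 34.83 being the unadjusted SD of PCH_T, and on the variance-reduction approximation. If rho is 0, the price is about one degree of freedom.

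Three stronger readings are not supported:

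- **A definite loss of 4 to 6 points.** That needs |rho| of about 0.39 to 0.49, and the documents give no value.
- **An underpowered trial or a biased p-value.** The 122 per arm and 90% reproduce, and the test is valid.
- **Baseline ignored altogether.** It is the divisor, and an adjusted analysis is prespecified with code. The issue is that this analysis is exploratory and not primary.

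**What to change.** Before unblinding, amend SAP 7.8.1 and Protocol 6.9.1 in one of two ways:

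1. Make the primary test a rank ANCOVA: rank PCH_T and baseline IA frequency per 7 days across the 36 mg and placebo subjects, regress the first on treatment and the second, and test treatment two-sided at 0.05.
2. Promote the randomization-based analysis of SAP 6.3 and 7.8.4 to primary, with baseline IA as a prespecified covariate.

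Keep the unadjusted Wilcoxon p-value as a supportive result and the Hodges-Lehmann difference with its 95% CI as the effect size. Rewrite the multiple-imputation and maintenance-only analyses (SAP 7.8.2, Protocol 6.9.4) so that they test the new primary analysis. A blinded, pooled estimate of rho would show the likely gain.

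No extra patients or data are needed. The cost is a protocol amendment, which Protocol 6.1 requires for a principal feature, plus the realignment of the sensitivity analyses. At the margin, the adjusted p-value may disagree with the unadjusted Hodges-Lehmann interval, and the SAP should state in advance that the adjusted p-value decides.
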